6.20.6 Limitations and Planned Solutions

If decolonization is successful, it is conceivable that isolation of MRSA and other bacterial pathogens may be substantially reduced, resulting in inadequate collection. In the event that this occurs, we will broaden the time window for isolate collection. Since our baseline period is 12-months and our intervention period is 18-months, (NOTE: intervention was extended to a 21-month trial in June 2015), the current plans to collect isolates for 9-months in each period still allows for additional collection time should it be necessary. We will monitor collection progress continually so that the collection period can be extended seamlessly, if this is needed.

6.30 Aim 3: Estimate the costs associated with the intervention (chlorhexidine + selective MRSA decolonization) and the attributable medical costs of healthcare associated infections in adult general inpatient units and infectious readmissions, in order to evaluate the potential for cost savings associated with the strategy of reducing bioburden to prevent infection.

Costs of healthcare associated infections (HAIs) have been studied mainly in academic medical centers.^{10 226 227 228 229 230} Estimates of HAI costs in community hospitals are needed since community hospitals represent the majority of inpatient care in the U.S., and costs may differ from academic hospitals.^{231 232 233} In addition, the cluster-randomized design affords an important and unique opportunity to assess the economic value of decolonization across a large number of hospitals. In particular, case mix differences between

hospitals can be closely adjusted for due to combination of several factors: 1) control group of hospitals with stratified randomization, 2) baseline data from each hospital, and 3) availability of individual patient adjusters from electronic health records and administrative data. In this aim, we will estimate the incremental hospital costs associated with the intervention and evaluate differences in total medical costs among patients with and without HAIs in the intervention and control arms. We will then estimate the net cost of medical care for the intervention and the control groups, adjusting for key health factors.

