The majority of healthcare-associated infections (HAIs) occur outside of ICUs, in general medical, surgical, and oncology units. The ABATE Infection Trial (**A**ddressing **B**ioBurden while **A**dmitted **T**o **E**liminate Infection) seeks to reduce these HAIs and the readmissions they cause to their lowest practicable level by reducing the reservoirs of the pathogens that cause most HAIs. This cluster-randomized trial will target all pathogens through bathing with chlorhexidine and additionally target carriers of methicillin-resistant *Staphylococcus aureus* (MRSA) through nasal decolonization with mupirocin. This intervention strategy will be compared to routine care in non-ICU medical, surgical, and oncology units.

This trial will assess a high yield strategy that is relevant to the large majority of hospitalized patients. If successful, this decolonization strategy would become best practice for preventing infection among 40 million patients hospitalized each year in the United States alone.

Specific aims for the Trial Intervention Phase are as follows:

- 1) Conduct a 50+-hospital cluster-randomized controlled trial of routine chlorhexidine bathing and selective MRSA decolonization versus standard-of-care practices for all hospitalized patients in non-critical care adult medical, surgical, and oncology units. The primary outcome will be clinical burden of gram-positive multi-drug resistant organisms. Secondary outcomes will include clinical burden of gram-negative multi-drug resistant organisms, bloodstream infections, and readmissions caused by infection.
- 2) Assess whether universal chlorhexidine bathing and selective MRSA decolonization result in increased resistance to chlorhexidine or mupirocin among bacterial strains collected during the trial.
- 3) Estimate the costs associated with the intervention (chlorhexidine + selective MRSA decolonization) and the attributable medical costs of healthcare associated infections in adult general inpatient units and infectious readmissions, in order to evaluate the potential for cost savings associated with the strategy of reducing bioburden to prevent infection

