6.10.6 Finalized Outcomes

Study outcomes were finalized following deliberation of the Steering Committee during the UH2 planning year. Deliberations included response to recent published literature, including the REDUCE MRSA Trial which was conducted by our investigative team.^{125 205} The primary outcome will be the presence of at least one clinical culture with gram-positive multi-drug resistant bacteria (MRSA and VRE) attributable to a participating unit. This outcome was solidified following recent clinical trial evidence of the success of chlorhexidine (with and without mupirocin) in reducing these pathogens in ICUs.^{125 205} An *a priori* secondary outcome intended for the primary manuscript is all-cause bloodstream infection attributable to a participating unit. Additional *a priori* secondary study outcomes intended for secondary manuscripts are provided in **Table 10**.

Table 10. Study Outcomes

Primary Outcome
MRSA and VRE clinical cultures ^a
Secondary Outcomes (Primary Manuscript)

All-cause bloodstream infection ^{a b}
Secondary Outcomes (Secondary Manuscripts)
Gram-negative multi-drug resistant organisms ^a
Urinary tract infections ^a
C difficile clinical tests ^a
Blood culture contamination
30-day infectious readmissions
Emergence of resistance to chlorhexidine or mupirocin ^a
Cost effectiveness

^a Attributable to participating units. Defined as occurring >2 days into a participating unit stay through 2 days following unit discharge

^b Includes subsets of GP and GN MDROs as well as key pathogens such as *S. aureus*

These outcomes are designed to maximize the evaluation of the impact of decolonization in non-critical care settings. They will address major concerns in healthcare related to reduction of antibiotic-resistant pathogens, and impact on a range of hospital-associated infections. They will also assess the likelihood that bacterial strains will develop resistance to chlorhexidine and mupirocin following broad use among inpatients.

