6.30.1 Cost Analysis Study Design

A cost analysis will be pursued with HCA health economist, [name]., if the ABATE Infection Trial demonstrates a significant beneficial effect in its primary outcome. If this occurs, we hypothesize that decolonization will be associated with reduced costs associated with hospitalization and readmission. We will take advantage of the cluster randomized trial design to test the hypothesis that the Decolonization Arm is associated with a significantly greater reduction in total medical costs between the intervention vs. baseline period when compared to the Usual Care Arm. Our study population will include adult patients in the trial who have spent time on a participating unit. In this population, we will assess the costs of the initial hospitalization and any subsequent infectious admission within 30 days following discharge.

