6.30.2 Data Sources

For overall hospitalization costs, we will obtain complete hospitalization charges from HCA financial data, which do not include intervention costs. HCA has highly standardized financial records where charges for hospital beds, procedures, and various drugs and supplies are aggregated to produce a total hospitalization charge. Since hospital charges do not reflect true costs that hospitals incur, we will apply hospital cost-to-charge ratios obtained from HCA to obtain total hospitalization costs per admission.

Intervention costs, which will not be included in HCA charge data, will be determined as follows. We will measure the volume of supplies used multiplied by a standard unit cost. For all participating hospitals, we will collect unit-specific dispensed daily doses of mupirocin and chlorhexidine product. Mupirocin dispensing will be obtained from pharmacy data and chlorhexidine usage will be obtained from daily bathing compliance data obtained during the trial. Standard unit costs for each of these will be obtained from the manufacturer, publicly available data, or published sources. Chlorhexidine costs will be calculated as the incremental costs over the unit costs of common non-chlorhexidine bathing supplies. This will be done in two ways to account for the two most common chlorhexidine products on the market. First, we will calculate the incremental cost of disposable chlorhexidine-impregnated bathing cloths (as used in this trial) compared to disposable bathing cloths. Second, we will assume all bed baths are performed using basin baths and will calculate the incremental costs of adding generic liquid chlorhexidine to basins compared to routine soap and water basin baths. Finally, we will assess differences in the amount of unit-specific gown and glove use based upon supply chain data between arms and between baseline and intervention periods. This will account for potential cost-savings due to decreased transmission from the intervention.

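### Aim 3's comparison of total cost with and without an HAI counts pre-infection cost as infection cost, so the attributable-cost estimate is biased upward

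*Protocol*

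**What the plan says.** Protocol section 6.30 (Aim 3) sets out to estimate "the attributable medical costs of healthcare associated infections in adult general inpatient units and infectious readmissions". The same aim appears in the UH3 Specific Aims. The introduction to section 6.30 gives one contrast for it: to "evaluate differences in total medical costs among patients with and without HAIs in the intervention and control arms".

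The pieces that define this contrast are spread over several sections:

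- **Cost.** Section 6.30.2 takes complete charges for the stay, "aggregated to produce a total hospitalization charge", and then states: "we will apply hospital cost-to-charge ratios obtained from HCA to obtain total hospitalization costs per admission". Section 6.30.1 adds infectious readmissions within 30 days of discharge.
- **Population.** Section 6.30.1: "Our study population will include adult patients in the trial who have spent time on a participating unit". No minimum individual stay is given there. The 2-day rule in section 5.10.3 concerns a unit's average stay.
- **When an event counts.** Section 6.10.6, Table 10, footnote a: "Defined as occurring >2 days into a participating unit stay through 2 days following unit discharge". Section 6.10.11 repeats the rule, and Aim 3 gives no other definition of an HAI.
- **Model.** Section 6.30.3 specifies a generalized linear mixed model with arm, period, their interaction, unit type, demographics and comorbidity. It has no infection date, no length of stay and no time-varying HAI term. Its only sensitivity analysis concerns deaths.
- **Limitations.** Section 6.30.5 mentions unmeasured confounding only.

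**The concern.** A patient must stay long enough to acquire an attributed infection, and the longer the stay, the more days at risk. Infected patients are thus selected for long stays before the infection does anything. If whole-admission cost is compared by HAI status, the cost of those earlier days falls on the infection side. The contrast then shows an excess even when infection adds no cost at all.

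Demographic and comorbidity terms do not repair this, because the fault lies in the timing of the exposure and not in who the patients are. The protocol applies the principle elsewhere: section 6.10.11 chooses proportional hazards for the infection outcomes because tenure in the unit varies. Section 6.30.3 drops the time-to-event model for cost and puts nothing in its place.

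At stake is a named Aim 3 result. Section 6.30 motivates it by the need for HAI cost estimates from community hospitals, and a published figure of that kind would be too high.

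**Working it through.** Aim 3 states no cost, sample size or power figure, so there is nothing of its own to reproduce. The check asks how many extra days the planned contrast would show if infection added none.

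**Inputs from the documents:** the attribution window (Table 10, footnote a), whole-admission cost (6.30.2) and the population (6.30.1).

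**Assumptions not in the documents:** mean stay m of 3 to 6 days; exponential stays, or gamma stays with shape 2 or 3; constant infection hazard inside the window; unit stay equal to hospital stay; cost proportional to days.

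**Formula.** Let L be the stay and R(L) the days at risk. With a small constant hazard and no effect of infection on stay, E[L | HAI] = E[L·R(L)] / E[R(L)]. The spurious excess is this minus the comparison-group mean.

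**Version A: risk from day 2 to discharge, R = max(L − 2, 0).**

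- Exponential: E[L | HAI] = 2 + 2m. Against all patients (mean m) the excess is m + 2, so 5 days at m = 3 and 8 days at m = 6. Against stays over 2 days (mean m + 2) it is m, so 3 to 6 days.
- Gamma with shape k, scale θ = m/k and x = 2/θ has these partial moments over L > 2:
  - P = e^(−x) Σ(j ≤ k−1) x^j/j!
  - E[L; L > 2] = kθ e^(−x) Σ(j ≤ k) x^j/j!
  - E[L²; L > 2] = k(k+1)θ² e^(−x) Σ(j ≤ k+1) x^j/j!
- Example, k = 3 and m = 3: these are 5, 19 and 84, each times e^(−2). So E[L | HAI] = (84 − 38)/(19 − 10) = 46/9 = 5.11. The excess is 5.11 − 3 = 2.11 against all patients, and 5.11 − 19/5 = 1.31 against stays over 2 days.

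**Version B: full window to 2 days after discharge, R = L.** This assumes complete capture after discharge, so it is an upper bound on this correction. The excess is Var(L)/m = m/k. With stays of 2 days or less dropped from both groups it is E[L² | L > 2]/E[L | L > 2] − E[L | L > 2]. That is m²/(m + 2) for exponential stays, and 84/19 − 19/5 = 0.62 for k = 3, m = 3.

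Spurious excess in days, from m = 3 to m = 6:

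| Risk window | Comparison group | Exponential | Gamma, shape 2 | Gamma, shape 3 |
|---|---|---|---|---|
| Day 2 to discharge | All without HAI | 5 to 8 | 2.90 to 4.25 | 2.11 to 2.91 |
| Day 2 to discharge | Stays over 2 days | 3 to 6 | 1.76 to 3.45 | 1.31 to 2.51 |
| Full window | All without HAI | 3 to 6 | 1.5 to 3 | 1 to 2 |
| Full window | Short stays dropped from both groups | 1.8 to 4.5 | 0.91 to 2.44 | 0.62 to 1.73 |

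Dropping short stays from the comparison group alone, under the full window, takes the smallest case (k = 3, m = 3) to 4 − 3.8 = 0.2 days. The sign is positive in every version.

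**Check by simulation.** Four million stays per setting were simulated with geometric or lognormal stays (log-SD 0.8), mean 4 to 6 days and risk from day 2 to discharge. Incidence was scaled to Table 7's all-pathogen bloodstream infection rate (894/104,852 = 85.3 per 10,000).

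- True excess 0: the whole-stay comparison gave 5.0 to 7.7 days, or 3.0 to 6.3 with comparators limited to stays over 2 days.
- True excess 4 days: it gave 9.0 to 11.7 days.
- Infected patients compared from the infection day with uninfected patients still present that day: −0.01 to 0.08 days when the truth was 0, and 3.99 to 4.08 when it was 4.

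**The case against.** The strongest reply is that the HAI contrast is one clause in an introduction, with no estimator attached. What the protocol does specify (hypothesis in 6.30.1, model in 6.30.3) is the arm-by-period contrast of total cost. That contrast does not condition on HAI status, so this bias does not touch it. This stands. It does not remove the point, because attributable HAI cost is a named result and the only contrast offered for it is biased if followed as written.

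Other parts of the reply also stand:

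- A reader might infer that savings per case averted will be inflated in favour of decolonization. Section 6.30.3 introduces that figure straight after the interaction test, and nothing ties it to the HAI contrast.
- A reader might take the adjustment for health factors in section 6.30 as the planned remedy. It belongs to the net-cost comparison of the arms.
- Short stays are not certain to be comparators. Section 5.40.4 says the study cohort requires exclusion of the first two days in a unit, which leaves the matter open.
- The window runs to 2 days after unit discharge, so a short unit stay does not mean zero risk. Allowing for this lowers the exponential excess from m + 2 to as little as m, for example from 6 to 4 days at m = 4.
- Aim 3's cost analysis runs only if the primary outcome shows a significant benefit (6.30.1), and it is meant for secondary manuscripts (Table 10).

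**Conclusion.** The concern holds for the HAI-attributable cost estimate and for nothing wider. As described, the comparison counts pre-infection cost as infection cost, and the bias is upward. The spurious excess is roughly 1 to 8 days. It falls below 1 day only for the narrower stay distributions, when short stays are dropped and the full window is counted together. The size rests on assumed mean stays, stay shapes and a constant hazard, and the documents give no daily cost to turn days into money. The direction did not change in any version computed.

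The stronger reading, that Aim 3's randomized cost comparison is invalid or that the trial's cost-saving claim is biased, is not supported. The arm-by-period test is unaffected, and the source of savings per case averted is unstated. No primary or bloodstream-infection inference is involved. The change should be made before the cost analysis is run.

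**What to change.** Replace the HAI versus no-HAI comparison in Aim 3 with a risk-set comparison:

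1. For each patient whose HAI culture falls on stay day t, select patients in the same hospital and trial period who are still in hospital and HAI-free on day t.
2. Compare total admission cost, and days after t, with case-mix adjustment. Matching on t equalizes days before infection but not daily cost, so the adjustment is still needed.
3. Use cost from day t onward only if dated charges can be obtained. Section 6.30.2 describes a total per admission, and Table 4 in section 5.40.2 lists no dated charges.
4. State which definition of an HAI Aim 3 uses.
5. State that savings per case averted comes from the arm-by-period contrast.

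Admission, discharge and culture collection dates are already requested in Table 4, so the cost is protocol wording and modest programming. The downside is a smaller attributable-cost figure.

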6.30.1 Cost Analysis Study Design

A cost analysis will be pursued with HCA health economist, [name]., if the ABATE Infection Trial demonstrates a significant beneficial effect in its primary outcome. If this occurs, we hypothesize that decolonization will be associated with reduced costs associated with hospitalization and readmission. We will take advantage of the cluster randomized trial design to test the hypothesis that the Decolonization Arm is associated with a significantly greater reduction in total medical costs between the intervention vs. baseline period when compared to the Usual Care Arm. Our study population will include adult patients in the trial who have spent time on a participating unit. In this population, we will assess the costs of the initial hospitalization and any subsequent infectious admission within 30 days following discharge.

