where i is a hospital, j is a person within the hospital, Arm and $Period$ are indicator variables and are = 0 for patients in a hospital in the control arm or baseline period and 1 if in the intervention arm or period. The overall hazard rate over time for person ij is defined as $\lambda_{ij}(t)$, a function of the baseline hazard $\lambda_0(t)$, which is similar to the intercept in a linear model, times the proportionality for that subject, which is defined by the covariates Arm_{ij} and $Period_{ij}$ and the associated parameters, as well as the frailty, γ_i . The frailties are closely analogous to the random effect in generalized linear mixed models, and account for the clustering (similarity of hazard) within a given hospital. The ultimate effect of the intervention is assessed through β_3 : as parameterized, if it is negative and has p-value < .05 (or 95% CI excluding 0) then the intervention reduces the risk of infection. We plan to assess the need for different frailties by hospital by period (instead of just by hospital), as well as additional clustering by unit within hospital. In addition, we will investigate the need to adjust for the stratified randomization scheme described above in **Section 6.10.53**

Subsequent analyses will include as-treated and covariate-adjusted models. Adjusted models will account for individual characteristics such as age, gender, comorbidities based upon ICD-9 codes, and receipt of intervention products. We will also account for unit type (step down, medical, surgical, etc.) and baseline bathing frequency if this is not balanced after randomization. All analyses will be performed using current versions of SAS (9.4, as of writing, SAS Institute, Cary NC) and/or R (3.0.2, as of writing).²¹⁴

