After the baseline period, we were able to re-estimate the power, using the data collected in the full baseline period. We used the bootstrap process outlined above, except that we used the observed 12-month data for the baseline. We assessed the power for the original proposal of an 18-month intervention and for a slightly extended 21-month intervention period, oversampling the observed 12-month baseline data as needed in each case (see Table 14). This updated power assessment was considered to be more accurate in that it used approximately three times as much real data—12 months vs. four months—compared to the original estimate. Furthermore, additional cleaning steps were applied to the 12 months of baseline data. In these new assessments we focused on an intervention effect of 20%. The power for the primary outcome was 99.9% (95% CI: 99.4-99.99%) with 18 or 21 months of follow-up. For all pathogen bacteremia, the power was 85% (95% CI: 83-87%) with 18 months follow-up and 89% (87-90%) with 21 months follow-up. The steering committee decided to use 21 months of follow up to ensure greater power with less common secondary outcomes and account for lessened effects at sites that may drop out of the trial.

Table 14: Revised Power and Exact 95% CI for Primary and Select Secondary Outcomes*

Analysis	Effect	Primary Outcome MRSA, VRE Clinical Cultures	All Pathogen Bacteremia
As-randomized, 18-mo	20%	99.9% (99.4% – 99.99%)	85% (83% – 87%)
As-randomized, 21-mo	20%	99.9% (99.4% – 99.99%)	89% (87% – 90%)

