6.30.3 Analysis

We will use an analytic approach similar to our primary outcome of MDRO organism from a clinical or screening culture attributed to a participating non-ICU unit, with the exception that we will model will the outcome of hospitalization cost. Rather than proportional hazard models with shared frailties, we will use generalized linear mixed models to evaluate whether the Decolonization Arm is associated with significant cost-savings when accounting for clustering by hospital. Since cost data are typically quite skewed, data transformation may be required to assure adequate fit of the outcome distribution. Models will be chosen to fit the distribution: negative binomial models, or possibly, normal distributions after log transformation, for example. Either approach reduces the impact of large outliers typical in cost data. Model terms will include arm, trial period (baseline vs intervention), their interaction, unit type (step down, medical, surgical, etc.), and demographic and comorbidity variables. The assessment of whether outcomes in one arm are significantly different from the other will be determined by the significance of this interaction term, which assesses whether the mean cost difference between the baseline and intervention period differs significantly between the two arms. If significant, we will calculate the mean cost savings per case averted.

We will additionally perform a sensitivity analysis to account for potential mortality effects on total hospitalization costs. To do this, we will assign a large fixed hospitalization cost to all deaths and assess if the model still predicts cost savings.

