**Table 1. Study Outcomes**

Primary Outcome
MRSA and VRE clinical cultures a
Secondary Outcomes (Primary Manuscript)
All-cause bloodstream infection a b
Secondary Outcomes (Secondary Manuscripts)
Gram-negative multi-drug resistant organisms a
Urinary tract infections a
C difficile clinical tests a
Blood culture contamination
30-day infectious readmissions
Emergence of resistance to chlorhexidine or mupirocin a
Cost effectiveness

a Attributable to participating units. Defined as occurring >2 days into a participating unit stay through 2 days following unit discharge

b Includes subsets of GP and GN MDROs as well as key pathogens such as *S. aureus*

These outcomes are designed to maximize the evaluation of the impact of decolonization in non-critical care settings. They will address major concerns in healthcare related to reduction of antibiotic-resistant pathogens, and impact on a range of hospital-associated infections. They will also assess the likelihood that bacterial strains will develop resistance to chlorhexidine and mupirocin following broad use among inpatients.

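### Aim 3 is stated without condition, but the cost analysis runs only after a significant primary result and savings per case averted only after a significant cost test

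*Protocol*

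**What the plan says.** The aim carries no condition. The UH3 Specific Aims and the heading of Protocol 6.30 both commit to estimating the cost of the intervention and the attributable cost of infections and infectious readmissions. The introduction to 6.30 adds: "We will then estimate the net cost of medical care for the intervention and the control groups, adjusting for key health factors". Protocol Table 10 and SAP Table 1 list "Cost effectiveness" among the a priori secondary outcomes, and Protocol Table 15 schedules the Aim 3 milestones. None of these places mentions a condition.

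Two conditions appear in the methods.

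- Protocol 6.30.1 pursues the cost analysis "if the ABATE Infection Trial demonstrates a significant beneficial effect in its primary outcome". Under 6.10.11 the primary criterion is a two-sided one with a direction: "if it is negative and has p-value < .05 (or 95% CI excluding 0) then the intervention reduces the risk of infection".
- Protocol 6.30.3 fits a generalized linear mixed model to hospitalization cost with an arm-by-period interaction, and then says: "If significant, we will calculate the mean cost savings per case averted".

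The SAP does not repeat either condition and describes no cost model. Neither document gives a power, a mean cost, a cost standard deviation or a between-hospital variance for the cost analysis.

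**The concern.** Read literally, 6.30.1 makes a prespecified outcome disappear when another outcome misses significance. What a hospital pays per patient for decolonization, and whether the net cost is positive, matter at least as much after a null primary result as after a positive one. Protocol 1.4 itself names meaningful incremental cost as one reason for testing the regimen outside ICUs.

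The condition also looks only at MRSA and VRE clinical cultures. Bloodstream infection is the secondary outcome chosen for the primary manuscript, and Protocol 6.10.12 says the 21-month extension was adopted partly to gain power for less common secondary outcomes. If bloodstream infection fell and the primary outcome narrowly missed, no cost analysis would follow.

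The condition in 6.30.3 is a different problem. A savings figure shown only when its own test is significant is selectively reported. If the test has low power, the figure is usually withheld, and it is too large on average when shown.

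**Working it through.** **1. The plan's own figure.** For the primary outcome at a 20% effect, Protocol 6.10.12 states: "The power for the primary outcome was 99.9% (95% CI: 99.4-99.99%) with 18 or 21 months of follow-up". This comes from a bootstrap of patient-level data, and the documents give no MRSA/VRE event rate or frailty variance, so it cannot be recomputed from inputs. Two consistency checks are possible.

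- *Table 14 interval.* If 999 of 1,000 replicates rejected (the number is not stated), the exact 95% interval is 99.44–99.997%, in line with the printed one.
- *Normal approximation for the log hazard ratio, tried on the initial Table 13.* Power of 92% at 20% implies SE = |log 0.8| / (1.960 + 1.405) = 0.2231 / 3.365 = 0.0663. At 10% this predicts Φ(0.1054/0.0663 − 1.96) = Φ(−0.37) = 35.5%, against a printed 33% (28–37%). At 30% it predicts over 99.9%, against 100%. The approximation is adequate.

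**2. Chance of meeting the 6.30.1 condition at current precision (Table 14).** Power of 99.9% at 20% implies SE = 0.2231 / (1.960 + 3.090) = 0.0442.

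- At a true 10% reduction: Φ(0.1054/0.0442 − 1.96) = Φ(0.42) = 66%. Over the printed interval for the 99.9% the range is about 56–76%.
- Alternatively, let the variance depend on events: (1 + 1 + 1/k + 1/(k(1 − r)))/E, where k is the ratio of intervention to baseline length and r the reduction. Fitting E at 18 months (k = 1.5) gives E ≈ 1,793. At 21 months (k = 1.75) and r = 0.10, SE = √(3.206/1,793) = 0.0423 and the probability is Φ(0.53) = 70%.

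The event-based version at 21 months gives the following. The last column is the mean log hazard ratio among significant beneficial results, divided by the true value.

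| True reduction | Condition met | Exaggeration of primary estimate |
|---|---|---|
| 20% | 99.9% | 1.00 |
| 15% | 97% | 1.02 |
| 10% | 70% | 1.20 |
| 5% | 23% | 2.1 |
| 0% | 2.5% | – |

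The condition fails more often than not only if the true reduction is below about 8%.

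**3. The 6.30.3 condition, illustration only.** The documents supply over 400,000 patients (Abstract), a non-ICU bloodstream infection rate of 85.3 per 10,000 (Table 7) and $10,000–20,000 for certain serious infections (1.2). The following are assumptions:

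- 400,000 admissions in total over both periods, split 12:21 months and equally by arm;
- a cost SD of $8,000–25,000;
- 20% of infections prevented;
- the 1.2 cost applied to every bloodstream infection;
- no hospital variance and no intervention cost, both of which favour the test;
- a comparison of mean costs in dollars.

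Then SE = SD × √(2/72,727 + 2/127,273) = SD × 0.00657, which is $53 at SD $8,000, $99 at $15,000 and $164 at $25,000. The expected saving is 0.20 × 0.00853 × $10,000–20,000 = $17–34 per admission. At SD $15,000, power is Φ(17.1/98.6 − 1.96) = 4% to Φ(34.1/98.6 − 1.96) = 5%. The difference needed for 80% power is 2.80 × SE, or $147–460 over the SD range.

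Widening the assumptions to 400,000–1,200,000 admissions and to 0.85–2.5% of admissions with a preventable infection gives savings of $17–100 and power of 3–91%. Power stays below 50% except in two of the most favourable combinations (71% and 91%). A saving shown only when significant would be inflated by a factor between about 1.05 and 23.

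**The case against.** A reader might infer that Aim 3 will usually return nothing and, when it does return something, will rest on an exaggerated effect. The documents do not support that reading, for four reasons.

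- **The first condition is very likely to be met at the planned effect.** The 33% power at a 10% effect in Table 13 comes from a 4-month sample, and Protocol 6.10.12 regards the 12-month re-estimate as more accurate. At the newer precision a 10% effect meets the condition about two times in three.
- **Failing the second condition does not empty the aim.** It withholds one ratio. Once the analysis runs, 6.30.3 places no condition on intervention cost, cost with and without infection, net cost by arm or the fitted interaction.
- **Exaggeration of the primary effect does not carry through to savings.** The cost model does not use the primary hazard ratio. That effect could enter only through the number of cases averted, the denominator, where overstatement would lower savings per case. Only selection on the cost test itself can inflate them.
- **It cannot be said that the cost test must fail.** Every power figure for it rests on an assumed SD. The $10,000–20,000 refers to surgical site infection, central line-associated bloodstream infection and pneumonia, so it is not a cost for all bloodstream infections and does not show that they cost more than a primary event. Section 6.30.3 also allows negative binomial or log-transformed models, and the illustration omits other infections, readmissions and glove and gown savings.

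It is also fair to say that doing an economic analysis only after demonstrated benefit is a resource choice, and that 6.10.10 reports product use in any event. These points limit the size of the problem. They do not reconcile 6.30.1 with an unconditional aim and an a priori outcome, and they do not justify reporting savings only when significant.

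**Conclusion.** The inconsistency is in the text and needs no assumption: Aim 3 and the listed outcome are unconditional, while 6.30.1 and 6.30.3 make the analysis and its savings figure depend on significance. At the 20% planning effect the first condition costs almost nothing, with 99.9% power and negligible exaggeration. At a true 10% effect it would leave Aim 3 unanswered about one time in three (pass probability 66–70%, from a normal approximation to Table 14). Under no effect it would do so 97.5% of the time.

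The second condition makes reporting of savings per case averted selective. The figure would probably often be withheld, and inflated when shown, but the extent cannot be fixed from the documents. This is a cheap improvement worth making, not a threat to the primary analysis.

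**What to change.** - **Protocol 6.30.1:** delete the condition on the primary outcome, so that intervention cost, infection-attributable cost and net cost by arm are estimated whatever the primary result.
- **Protocol 6.30.3:** replace "If significant, we will calculate the mean cost savings per case averted" with wording such as: *The arm-by-period difference in mean cost per patient, net of intervention cost, will be reported with its 95% confidence interval in all cases.* The net term needs to be explicit because 6.30.2 says the charge data exclude intervention costs.

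The cost is protocol wording and modest analyst time. Charges and intervention costs are already in the Table 15 milestones, and 6.30.2 already sets out how product use will be measured. The real commitment is that a cost result must be published even if it is unfavourable.
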